Hu5F9-G4 treatment may be temporarily suspended in patients experiencing toxicity considered to be related to study treatment (see the Dose Modifications section). If a patient misses three or more consecutive doses during the combination treatment period, the investigator and Medical Monitor will decide whether the patient should discontinue Hu5F9-G4 permanently. If Hu5F9-G4 is withheld for > 28 days because of toxicity, the patient should be discontinued from Hu5F9-G4. However, if the investigator believes the patient is likely to derive clinical benefit and the Medical Monitor is in agreement, Hu5F9-G4 can be resumed after being withheld for > 28 days. If the time interval between Hu5F9-G4 doses is > 4 weeks on account of missed doses, a repriming period is required prior to restarting weekly doses. If repriming is necessary, atezolizumab should be held during the repriming week and restarted when the 30-mg/kg weekly dosing of Hu5F9-G4 begins.

If atezolizumab is discontinued, Hu5F9-G4 should also be discontinued. If Hu5F9-G4 is discontinued, atezolizumab can be continued if the patient is likely to derive clinical benefit, as determined by the investigator.

MANAGEMENT GUIDELINES

Guidelines for the management of patients who experience specific adverse events are provided in [Appendix 9](#) for atezolizumab-related adverse events and in the Atezolizumab Investigator's Brochure. This section integrates management guidelines for those adverse events when both atezolizumab and Hu5F9-G4 have developed guidance. This section also includes generic guidance for management of Hu5F9-G4.

Appendix 8

Overall Guidelines for Management of Patients Who Experience Adverse Events (cont.)

when atezolizumab-associated adverse events occur. This section includes management guidelines for Hu5F9-G4-associated adverse events. For cases in which management guidelines are not covered in [Appendix 9](#), the Hu5F9-G4 Investigator's Brochure, or the protocol, patients should be managed as deemed appropriate by the investigator according to best medical judgment.

INFUSION-RELATED REACTIONS AND ANAPHYLAXIS

Management guidelines for patients who experience infusion-related reactions or anaphylaxis are presented in [Table 1](#).

Table 1 Guidelines for Management of Patients Who Experience Adverse Events Associated with Hu5F9-G4

Event	Action to Be Taken
IRRs and anaphylaxis	

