IRR, Grade 3 or 4	
 • Follow guidelines for atezolizumab in Appendix 9. • For anaphylaxis precautions, see Appendix 7. • For Hu5F9-G4: 
 – Stop infusion and permanently discontinue Hu5F9-G4. – Begin an IV infusion of normal saline, and treat the patient as follows: administer bronchodilators, epinephrine 0.2 to 1 mg of a 1:1000 solution for SC administration or 0.1 to 0.25 mg of a 1:10,000 solution injected slowly for IV administration, and/or diphenhydramine 50 mg IV with methylprednisolone 100 mg IV or equivalent, as needed. – Administer aggressive symptomatic treatment. – All patients will be observed for an additional 24 hours or longer until the adverse event resolves, with vital sign measurements every 4 hours and additional evaluations as medically indicated for the management of the adverse event.
Atezolizumab-related toxicities not described above	
Grade 1 or 2	
 • Follow guidelines for atezolizumab in Appendix 9. • Continue Hu5F9-G4.
Grade 3	
 • Follow guidelines for atezolizumab in Appendix 9. • Continue Hu5F9-G4.
Grade 4	
 • Follow guidelines for atezolizumab in Appendix 9. • Hu5F9-G4 may be continued at the discretion of the investigator per medical judgment.

IRR=infusion-related reaction.

Hu5F9-G4-ASSOCIATED ANEMIA

Anemia, Blood Crosmatching, and Packed RBC Transfusion Procedures

Hu5F9-G4 binds to RBCs and leads to erythrophagocytosis. This, coupled with anemia from other cause in patients with cancers, means that care has to be taken with RBC crossmatching and packed RBC transfusions. There is a possibility that treatment with Hu5F9-G4 may obscure assessment of RBC phenotyping, although this has not been observed in patients to date.

Appendix 8

Overall Guidelines for Management of Patients Who Experience Adverse Events (cont.)

At baseline, prior to initiation of Hu5F9-G4 therapy, blood cell ABO phenotyping for minor antigens, type, and screen (ABO blood type and Rhesus [Rh] factor), and direct antibody testing (DAT) will be performed to facilitate, together with the prior phenotype, allocation of properly crossmatched blood in the event a blood transfusion is warranted.

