Dyspnea, cough, fatigue, hypoxia, pneumonitis, and pulmonary infiltrates have been associated with the administration of atezolizumab. Patients will be assessed for pulmonary signs and symptoms throughout the study and will also have computed tomography (CT) scans of the chest performed at every tumor assessment.

All pulmonary events should be thoroughly evaluated for other commonly reported etiologies such as pneumonia or other infection, lymphangitic carcinomatosis, pulmonary embolism, heart failure, chronic obstructive pulmonary disease, or pulmonary hypertension. Management guidelines for pulmonary events are provided in [Table 1](#).

Appendix 9

Risks Associated with Atezolizumab and Guidelines for Management of Adverse Events Associated with Atezolizumab (cont.)

Table 1 Management Guidelines for Pulmonary Events, Including Pneumonitis

Event	Management
Pulmonary event, Grade 1	
 • Continue atezolizumab and monitor closely. • Re-evaluate on serial imaging. • Consider patient referral to pulmonary specialist.
Pulmonary event, Grade 2	
 • Withhold atezolizumab for up to 12 weeks after event onset.^a • Refer patient to pulmonary and infectious disease specialists and consider bronchoscopy or BAL. • Initiate treatment with corticosteroids equivalent to 1–2 mg/kg/day oral prednisone. • If event resolves to Grade 1 or better, resume atezolizumab.^b • If event does not resolve to Grade 1 or better while withholding atezolizumab, permanently discontinue atezolizumab and contact Medical Monitor.^c • For recurrent events, treat as a Grade 3 or 4 event.
Pulmonary event, Grade 3 or 4	
 • Permanently discontinue atezolizumab and contact Medical Monitor.^c • Bronchoscopy or BAL is recommended. • Initiate treatment with corticosteroids equivalent to 1–2 mg/kg/day oral prednisone. • If event does not improve within 48 hours after initiating corticosteroids, consider adding an immunosuppressive agent. • If event resolves to Grade 1 or better, taper corticosteroids over ≥ 1 month.

BAL = bronchoscopic alveolar lavage.

- ^a Atezolizumab may be withheld for a longer period of time (i.e., > 12 weeks after event onset) to allow for corticosteroids (if initiated) to be reduced to the equivalent of ≤ 10 mg/day oral prednisone. The acceptable length of the extended period of time must be agreed upon by the investigator and the Medical Monitor.

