
^b If corticosteroids have been initiated, they must be tapered over ≥ 1 month to the equivalent of ≤ 10 mg/day oral prednisone before atezolizumab can be resumed.

^c Resumption of atezolizumab may be considered in patients who are deriving benefit and have fully recovered from the immune-mediated event. Patients can be re-challenged with atezolizumab only after approval has been documented by both the investigator (or an appropriate delegate) and the Medical Monitor.

Appendix 9
Risks Associated with Atezolizumab and Guidelines for Management of Adverse Events Associated with Atezolizumab (cont.)

Table 2 Management Guidelines for Hepatic Events (cont.)

Event	Management
Hepatic event, Grade 3 or 4	
• Permanently discontinue atezolizumab and contact Medical Monitor.^c• Consider patient referral to gastrointestinal specialist for evaluation and liver biopsy to establish etiology of hepatic injury.• Initiate treatment with corticosteroids equivalent to 1–2 mg/kg/day oral prednisone.• If event does not improve within 48 hours after initiating corticosteroids, consider adding an immunosuppressive agent.• If event resolves to Grade 1 or better, taper corticosteroids over ≥ 1 month.

LFT = liver function test.

- ^a Atezolizumab may be withheld for a longer period of time (i.e., > 12 weeks after event onset) to allow for corticosteroids (if initiated) to be reduced to the equivalent of ≤ 10 mg/day oral prednisone. The acceptable length of the extended period of time must be agreed upon by the investigator and the Medical Monitor.
- ^b If corticosteroids have been initiated, they must be tapered over ≥ 1 month to the equivalent of ≤ 10 mg/day oral prednisone before atezolizumab can be resumed.
- ^c Resumption of atezolizumab may be considered in patients who are deriving benefit and have fully recovered from the immune-mediated event. Patients can be re-challenged with atezolizumab only after approval has been documented by both the investigator (or an appropriate delegate) and the Medical Monitor.

GASTROINTESTINAL EVENTS

Immune-mediated colitis has been associated with the administration of atezolizumab. Management guidelines for diarrhea or colitis are provided in [Table 3](#).

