- ^b If corticosteroids have been initiated, they must be tapered over ≥ 1 month to the equivalent of ≤ 10 mg/day oral prednisone before atezolizumab can be resumed.
- ^c Resumption of atezolizumab may be considered in patients who are deriving benefit and have fully recovered from the immune-mediated event. Patients can be re-challenged with atezolizumab only after approval has been documented by both the investigator (or an appropriate delegate) and the Medical Monitor.

Appendix 9

Risks Associated with Atezolizumab and Guidelines for Management of Adverse Events Associated with Atezolizumab (cont.)

Table 3 Management Guidelines for Gastrointestinal Events (Diarrhea or Colitis) (cont.)

Event	Management
Diarrhea or colitis, Grade 4	
 • Permanently discontinue atezolizumab and contact Medical Monitor.^c • Refer patient to GI specialist for evaluation and confirmation biopsy. • Initiate treatment with corticosteroids equivalent to 1–2 mg/kg/day IV methylprednisolone and convert to 1–2 mg/kg/day oral prednisone or equivalent upon improvement. • If event does not improve within 48 hours after initiating corticosteroids, consider adding an immunosuppressive agent. • If event resolves to Grade 1 or better, taper corticosteroids over ≥ 1 month.

GI = gastrointestinal.

- ^a Atezolizumab may be withheld for a longer period of time (i.e., > 12 weeks after event onset) to allow for corticosteroids (if initiated) to be reduced to the equivalent of ≤ 10 mg/day oral prednisone. The acceptable length of the extended period of time must be agreed upon by the investigator and the Medical Monitor.
- ^b If corticosteroids have been initiated, they must be tapered over ≥ 1 month to the equivalent of ≤ 10 mg/day oral prednisone before atezolizumab can be resumed.
- ^c Resumption of atezolizumab may be considered in patients who are deriving benefit and have fully recovered from the immune-mediated event. Patients can be re-challenged with atezolizumab only after approval has been documented by both the investigator (or an appropriate delegate) and the Medical Monitor.

ENDOCRINE EVENTS

Thyroid disorders, adrenal insufficiency, diabetes mellitus, and pituitary disorders have been associated with the administration of atezolizumab. Management guidelines for endocrine events are provided in [Table 4](#).

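### Appendix 8 gives opposite Hu5F9-G4 instructions when atezolizumab is permanently stopped below Grade 4, and its atezolizumab restart trigger after repriming cannot be met at 15 mg/kg or by a patient kept at 20 mg/kg.

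*Combined protocol and SAP*

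**What the plan says.** **Stopping Hu5F9-G4.** The Treatment Interruption text of Appendix 8 gives a rule with no exception by event or grade: "If atezolizumab is discontinued, Hu5F9-G4 should also be discontinued". The next sentence covers the reverse case and does allow an exception: if Hu5F9-G4 stops, atezolizumab may go on where the investigator expects benefit.

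Table 1 of Appendix 8 has rows for atezolizumab-related toxicities other than infusion reactions and anaphylaxis. Each row sends the reader to Appendix 9 for atezolizumab. For Hu5F9-G4, the Grade 1 or 2 row and the Grade 3 row both say "Continue Hu5F9-G4". The Grade 4 row says "Hu5F9-G4 may be continued at the discretion of the investigator per medical judgment".

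For a set of serious immune-mediated events, the action in Appendix 9 is "Permanently discontinue atezolizumab and contact Medical Monitor".

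**Restarting atezolizumab.** The same Appendix 8 text requires repriming when more than 4 weeks separate Hu5F9-G4 doses. Atezolizumab is held in the repriming week and restarts when weekly Hu5F9-G4 at 30 mg/kg begins. Section 3.1.2.2 sets maintenance in the de-escalation cohort at 15 mg/kg weekly. The Dose Modifications text of Appendix 8 allows an individual reduction to 20 mg/kg. Section 4.3.2.2 bases repriming on the patient's original regimen and gives the 30 mg/kg schedule as an example.

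**The concern.** A site treating, say, a Grade 3 pneumonitis must stop atezolizumab permanently under Appendix 9. On Hu5F9-G4 it then finds one sentence in Appendix 8 telling it to stop and a table row in the same appendix telling it to continue. Section 5.1.3 names pulmonary, hepatic, ocular, cardiac, neurologic and renal events, meningoencephalitis, HLH and MAS as potential overlapping toxicities of the two drugs, and says that the effect of combining them is unknown. These are the events on which the instructions disagree. With 6 to 10 sites and at most 21 patients, different readings would also give uneven Hu5F9-G4 exposure after the events of most safety interest.

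The restart rule is a separate problem. Followed exactly, it leaves a patient on the 15 mg/kg regimen without atezolizumab indefinitely after repriming, although the study is of the combination.

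**Working it through.** The plan states no figure on this point, so the check sets the rules side by side and adds a short count.

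**1. Where the Hu5F9-G4 rules meet.** Rows are events for which Appendix 9 requires permanent atezolizumab discontinuation.

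| Event (Appendix 9 table) | Grades affected | Appendix 8 Table 1 | Treatment Interruption text | Can both be followed? |
|---|---|---|---|---|
| Pulmonary (1), hepatic (2), ocular (5), myocarditis (6), neuropathy (10), renal (12) | 3 | Continue | Stop | No |
| Myasthenia gravis or Guillain-Barré syndrome (10), meningoencephalitis (11) | Any grade below 4 | Continue | Stop | No |
| Suspected HLH or MAS (14), no grade limit given | Any grade below 4 | Continue | Stop | No |
| Any of these at Grade 4, and events stopped permanently only at Grade 4, such as "Diarrhea or colitis, Grade 4" | 4 | May continue | Stop | Yes, by stopping |

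There is no conflict while atezolizumab is only withheld, because the stop sentence is then not triggered. Nor is there one for Grade 3 or 4 infusion reactions, where Table 1 itself stops Hu5F9-G4 permanently.

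**2. Which weekly doses reach the restart trigger.**

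| Regimen (mg/kg) | Weekly dose | Reaches 30 weekly? |
|---|---|---|
| Initial: 1, 1, 15, 30, then weekly | 30 | Yes |
| De-escalation: 1, 1, 10, 15, then weekly | 15 | Never |
| Reduced and kept at 20 | 20 | Never |
| Reduced to 20, then reprimed on the original regimen (Section 4.3.2.2) | 30 | Yes, but the reduction is undone |

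**3. How many patients could be on 15 mg/kg.** The de-escalation cohort has 6 patients and, if that dose is tolerated, its expansion cohort has 9: 6 + 9 = 15 of the 21 allowed. This is a maximum, since replaced patients count toward the cap.

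**4. How likely that cohort is to open.** It opens with 2 or more DLTs in the first 6 patients. With true DLT rate *p*, P(open) = 1 − (1−p)^6 − 6p(1−p)^5. The documents give no expected DLT rate, so *p* is assumed:

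- p = 0.10: 1 − 0.5314 − 0.3543 = 0.114
- p = 0.20: 1 − 0.2621 − 0.3932 = 0.345
- p = 0.30: 1 − 0.1176 − 0.3025 = 0.580

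These are chances that the 15 mg/kg regimen is used at all. For the defect to matter, a patient must also miss more than 4 weeks and resume.

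**The case against.** **The rules can be reconciled.** Appendix 8 describes its own content in these terms: "This section also includes generic guidance for management of Hu5F9-G4". One can argue that the specific stop sentence outranks generic rows, that these Appendix 9 rows generally require Medical Monitor contact, and that Section 4.6.1 already stops both drugs for intolerable related toxicity. This limits the risk to patients. It does not settle the rule: the generic guidance is meant for the very situation in which atezolizumab-associated events occur, and no text ranks the two instructions. The appendix's fallback to best medical judgment is for cases that the guidelines do not cover, whereas here two guidelines cover the case. The rechallenge footnotes in Appendix 9 concern only atezolizumab.

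**The scope is narrower than it looks.** A reader might infer that every permanent-discontinuation row conflicts. The documents do not support that. At Grade 4, Table 1 is permissive, so stopping satisfies both texts. Appendix 9 also has rows of the form "If event does not resolve to Grade 1 or better while withholding atezolizumab, permanently discontinue atezolizumab and contact Medical Monitor"; these, and recurrent events, can be read in sequence: Hu5F9-G4 continues while atezolizumab is withheld, and the stop sentence applies once atezolizumab ends. This part of the objection stands.

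**The restart lock-out is unlikely in practice.** The hold is described as lasting the repriming week, three or more consecutive missed doses already call for a decision with the Medical Monitor, and more than 28 days off Hu5F9-G4 for toxicity leads to discontinuation by default. So an unnoticed lock-out is improbable. But the stated condition for restarting remains one that the 15 mg/kg regimen cannot meet. The 20 mg/kg case is conditional, as the working shows.

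**Conclusion.** Both errors stand. The first is a direct contradiction confined to the events below Grade 4 listed in the working; at Grade 4 there is a tension only. The second is unconditional at 15 mg/kg, which could apply to up to 15 of 21 patients if that dose opens and is tolerated. At 20 mg/kg it depends on the reduction being kept.

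A reader might want an expected number of affected patients. The documents do not support one. The discontinuation rates in Sections 1.2.4 and 1.4 (5.4% and 10%) are for any adverse event on single-agent atezolizumab, and the share passing through a conflicting row is not given. No repriming frequency is given, and repriming cannot safely be treated as independent of DLTs, because missing the next scheduled dose through related toxicity in the DLT window is itself a DLT (Section 3.1.2.1).

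A reader might also infer that the DLT count is disturbed. It should not be: a related event leading to withdrawal is already a DLT under Section 3.1.2.3. No endpoint, sample size or error rate is affected. The point concerns dosing and safety conduct, and it deserves correction because following the text exactly gives either opposite instructions or no route back to the combination.

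**What to change.** 1. Add to the Table 1 rows for atezolizumab-related toxicities: *unless atezolizumab is permanently discontinued, in which case discontinue Hu5F9-G4*. This is the safer default, given the overlapping toxicities listed in Section 5.1.3. Its small downside is that the investigator loses discretion at Grade 4 once atezolizumab has been permanently stopped. If the sponsor intended the opposite, the exception should instead be written into the Treatment Interruption sentence. Either way, one rule should remain.
2. In the repriming sentence, replace the 30 mg/kg trigger with *the patient's assigned weekly maintenance dose*. Weekly doses of 30, 20 and 15 mg/kg can then all meet it.

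The cost is amendment wording only: no extra patients, visits or procedures.
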